Treatment Fidelity and Subject Expectancy. Assuring treatment fidelity (clinician) is important in clinical trials. This may be accomplished by various methods, dependent on trial design, and often involves standard training, random checks by live or taped observation, and ongoing training to promote reliability. With one practitioner, accuracy and consistency is required, but of course there is no need for inter-therapist reliability. First, the study acupuncturist hired will be well-trained, research experienced, and further trained on study protocol by Dr's. [name] and [name]. At least five volunteer patients using each ACU and MIN will be treated and observed; landmarks, needle insertion and manipulation, electrical stimulation, and needle removal will be judged and discussed for each case. Second, non-specific elements of the intervention, such as instructions for treatment preparation, and interactions during treatment will be reliably delivered by using clinical scripts adapted from our first study. Third, all treatment sessions will be videotaped. The first 5 and a random selection of 15% (18 total cases) thereafter chosen by a computer randomizer will be scored by study assessor supervised by [name] using the Fidelity Assessment Rating Form adapted for this study. Dr's. [name] and [name] will provide feedback to the acupuncturist about improvement. We will use scores to explore score effects by group.

It is important to assess effects of treatment expectancy on outcomes. We do not want to encourage subject learning about type of intervention, so will not assess expectancy after each session. Rather, we will assess treatment credibility (Borkovec, 1972) as has been done in previous acupuncture studies before session 1 and after sessions 2 and 24, and explore effects of expectancy by group and total sample on outcome.

Demographic and Other Data. A demographic and other data form will be developed for this study to assess important information for matching and data analyses: age, gender, ethnicity, combat history, medical history, medications, potential head injury, exposures to toxic chemicals, and current treatment.

Human Subjects Detail

Human Subjects Involvement and Characteristics: This study will utilize a longitudinal randomized design to evaluate the efficacy of 12-week manualized verum acupuncture (ACU) for PTSD in combat Veterans. The primary outcome will be the pre-to post-treatment change in PTSD symptom severity. The secondary outcome will be a peripheral physiological response (PPR) of startle response to a stimulus. Exploratory outcomes will be other PPR indices (biological) and clinical conditions that are associated with PTSD. Potential subjects will be recruited from the Long Beach Veterans Affairs Healthcare System (LBVA) and associated Veteran organizations. We will randomize 90 subjects into the two study groups of 45 each: subjects will be randomized to either: (1) verum acupuncture (ACU), or (2) placebo minimal needling (MIN).

Potential risks: The general risks are primarily psychological. Being asked to recall adverse life events or distressing symptoms in the diagnostic interview may compound the distressing nature of PTSD. However, interviews with survivors of torture and related trauma have found that testimony about traumatic experiences can be therapeutic (Cienfuegos and Monelli 1983; Agger and Jensen 1990; Thompson and McGorry 1995). There is evidence that trauma disclosure is helpful physically and psychologically over time, although in the short-term symptoms of depression may increase (Pennebaker and Susman 1988). The likelihood of the study worsening PTSD is small, since by the nature of the disorder, those who have PTSD will already be “experiencing” their trauma in a variety of ways, and all subjects will be provided with one EBT, the medication paroxetine. Study personnel need to be attentive to population and individual responses.

The physical risks include those from acupuncture, which includes minor bruising, hematoma and bleeding, fainting or nausea. There is a less than 1 in 10,000 risk of pneumothorax, and the reports of this are when the procedure was conducted by inexperienced clinicians. There is no reported risk from the psychophysiological assessment, although the stimulus (an air blast to the neck) is meant to be aversive, and participants have in other studies not wanted to return for testing.

Research risk: PTSD is a chronic illness that creates vulnerability and can lead to potential exploitation of subjects. The study includes interviews and questionnaires about PTSD symptoms and potentially traumatic combat experiences, as well as about other psychiatric symptoms and life events. In many studies involving the collection of information for gaining knowledge (e.g., biological markers), participants may not receive intervention for the condition under study. In this study, 45 subjects with PTSD will receive ACU, an intervention supported by current VA/DOD treatment guidelines for PTSD. Forty-seven will receive MIN, a placebo intervention. There is risk that their PTSD will go untreated, though study protocol will allow evidence-based medication if they are on them at a stable dose for ≥ 8 weeks. There is the risk that any participant will not improve but will either continue to have similar or higher levels of distress and symptoms.

Audio-Video Taping: Subjects will be asked to sign an informed consent to be taped. This consent will detail the use of the tapes (that they will be reviewed for provider treatment review), and that the tapes will be erased after the scoring for treatment fidelity is completed

There is a risk of non-effectiveness. This is more likely to be true for the MIN subjects.

Sources of Materials

Training materials. Any training materials will be available for study staff to use during the project. These materials are products of the project and will be kept in locked offices at the LBVA research offices throughout and after the end of the project.

Participant rosters. The electronic and hard copy rosters with full identifiers (participant names, addresses, and phone numbers) that can be linked to study and treatment ID numbers will be kept in locked file cabinets in research offices that are locked after hours at the LBVA. The electronic files will be password protected. At the end of the project only two copies of the research rosters will be kept in separate locked cabinets at the LBVA

research offices. Original rosters that connect ID numbers with participant identifiers will be destroyed at the end of the project. Electronic and hard copy rosters after the end of the project will be thus de-identified.

Data. Scores and data from psychological and physiological testing will be recorded and utilized solely for research purposes. All data will be entered into an electronic database at LBVA as the project progresses, and similar backup procedures will be employed. All hard copies of data will be marked only with a Study Identification number (SID#) and will be kept in a locked file cabinet in a space that is separate from participant rosters. After the hard copy questionnaire data is entered into the electronic database all original hard copies will be kept in locked research offices at LBVA. Final biological data that is analyzed or reviewed by any of our consultants at other institutions will only be identifiable by SID # and a date of collection number. These data will be sent between institutions by a passcode protected and encrypted email. Data are backed up each day on the main server at the LBVA.

Data Management Plan. The study data analyst (DA) will develop spreadsheets for each assessment in EXCEL under the supervision of the PI and the statistical consultants. The physiological data will be formatted for entry into ASCII files, which can be transferred to either EXCEL or MATLAB sources. The DA will enter and double check all data into respective spreadsheets as the data are collected. Once data entry is completed and merged into the primary database, transfer into SPSS or SAS files will be conducted and initial data runs will be performed to investigate data integrity. Once data integrity is determined, an original set of data files will be stored as "original" in case other iterations are harmed, altered, or lost. All electronic data files will be passcode protected, and only SID numbers and not other identifiers will be on each spreadsheet.

Compensation Plan. Our research team has consulted with participants and professional advisors to determine compensation for participants in this project. The amounts allocated (\$25 for initial assessment, \$150 for all biological assessments, \$25 for follow-up assessment, and \$50 for participating in the clinical trial) were thought to be fair given the level of participation and the potential benefit of intervention, and are intended to not be exploitative either from being insufficient for the time and effort spent, or as being coercive by being too large a sum.

2. Adequacy of Protection from Risk

Recruitment and Informed Consent

The methods of recruitment, informed consent, interviewing, and other assessment is intended to be protective for the participants, as they are potentially vulnerable to exploitation and harm given their medical/psychiatric status. We are attentive to ethical protections by: 1) following guidelines for ethically sound research, and 2) by having the capacity at LBVA to review research forms and treatment protocols from both a scientific and ethical perspective. Finally, we will encourage participants to ask questions and include family and friends in the informed consent decision process.

The process of obtaining informed consent is conducted at the Program for Traumatic Stress or a designated research office located at LBVA. Only authorized and properly trained study personnel by the PI are permitted to participate in the actual consent process. Potential subjects will be asked by research staff if he is interested in participating in the study. If he is interested, research staff will conduct education and ascertain if he wishes to participate. If the potential subject agrees to participate, the subject will be asked to provide informed consent.

Potential subjects will be asked if s/he can understand the consent form by reading the first paragraph. Qualified study personnel will then fully explain each section of the consent form in detail and will ask the potential subject to follow-along with another copy of the consent form. All potential subjects will be properly informed about the purpose of the study, study procedures, and the potential risks and benefits of being a participant. Each potential subject will affirm his or her understanding of each section prior to moving on to the next, and then will be given a copy of the consent form to also read at his leisure. The qualified research

Protocol Rev 3. 4.10.2018 MH

personnel will then ask the subject a number of open-ended questions about his level of understanding to ensure he has processed the information.

Once all questions have been asked and answered to each party's satisfaction, the consent form will be signed by the potential research subject and the qualified study personnel. If a potential subject wishes to think about participation, he will be encouraged to take the consent home, think about it, and discuss it with anyone whom he has a close personal relationship with to assist in making a decision. It will always be stressed that participation is fully voluntary and does not compromise care provided by the LBVA and the Program for Traumatic Stress. If the potential subject agrees to participate in the study, the PM will obtain written informed consent; the subject will be given a signed and dated copy of the consent form for his record. Once informed consent has been obtained, a screening for inclusion and exclusion criteria will be conducted to confirm eligibility for the study. The PM, who obtained informed consent, will document into the subject's electronic file in Computerized Patient Record System (CPRS) that informed consent was obtained.

Protections Against Risk

All research team members, including investigators, consultants, contractors and staff will be asked to sign a statement that details their conduct regarding participant confidentiality. This statement details consequences to team members for breach of confidentiality.

Our research staff is or will be trained to be open to participant questions and concerns. The participants will be encouraged to have an ongoing discussion and dialogue with the clinicians and staff. It will be made clear to each participant in the informed consent process and beyond that participation is voluntary, and that he may withdraw at any time without adverse consequences to his usual health care.

We recognize the variability of individual responses to answering questionnaires and interview questions related to PTSD, other life events, symptoms, and current health and social status. Team members will be sensitive and helpful to any individual participant who is distressed, whether or not the distress is from a research effect. The PM at LBVA is very experienced with and will field all calls and inquiries from participants about urgent treatment needs. If it is PTSD or study related, the PM will immediately troubleshoot the potential problem with the PI. If it is emergent, the PM will help the participant make a plan for a visit, which may include calling emergency transportation.

Adverse effects are extremely rare when acupuncture is performed in a professional setting by a fully trained and certified acupuncturist. Four out of the 5 deaths that have been associated with acupuncture in the literature were not equivocally due to acupuncture or were either self administered or administered by an untrained person. Possibilities of cross-infection will be avoided by using disposable needles and following clean-needle technique procedures. Other adverse effects will be avoided by using a fully trained and licensed acupuncturist who will practice in a professional setting.

The risk of non-effectiveness is mitigated by subjects being allowed to be taking medications for symptoms of PTSD and related conditions. Participants will be seen twice per week for protocol, and will be assessed each visit for aggression and suicidal ideation. Rules for withdrawal from study because of symptoms and/or potential danger to self or others will be part of protocol.

The video tapes will be destroyed after they have been reviewed for treatment fidelity.

Any adverse events will be documented and reported to proper authority. All research staff has been or will be trained in and abide by ethical research methods and good clinical practices.

3. Potential Benefits

There may be no direct benefit for a person to participate in this study, although we hypothesize benefit to subjects in the ACU group. The risks are minimal but present. For this study, an emphasis on informed consent

and safety is important. Results from this study are intended to provide a better understanding of the effects of acupuncture on PTSD and on peripheral psychophysiology. This information may enhance knowledge of and shape the treatment for PTSD which may potentially help thousands of veterans suffering from this illness.

4. Importance of Knowledge to be Gained

This study will improve knowledge about the use of acupuncture for PTSD, and will inform the field and policy makers about how acupuncture may be useful treatment for symptoms and biological functioning. Research evaluating how abnormal biological function in PTSD might be reversible with intervention is rare, and this study will help us understand what is reversible and what is not. This may improve our knowledge about mechanisms of treatment, and perhaps provide insight into risk factors. This will hopefully provide potential biological targets for further study.

5. Data and Safety Monitoring

Subjects will be given a sequential ID number that does not identify their PTSD status or their group assignment. Electronic and hard copy rosters with full identifiers (participant names, addresses, and phone numbers) that can be linked to study numbers will be kept in locked file cabinets in research offices that are locked after hours at LBVA. The electronic files will be password protected. At the end of the project, original rosters that connect ID numbers with participant identifiers will be destroyed.

In past studies in other settings we have constructed an internal Data and Safety Monitoring Committee or Board depending on the trial. We recognize and are pleased to know that, with funding via a Merit Review from CSR&D, we are eligible to use the services of the Centralized Data Monitoring Committee (DMC), and we are pleased that this study will have the availability of oversight by a CSR&D Centralized DMC panel.

The study protocol and requests for research review are pending submission to the Institutional Review Board at the VA Long Beach Healthcare System. The IRB at the VA Long Beach meets twice a month, and so the protocol will be able to be reviewed and appropriately approved within the first three months after funding.

To ensure adequate subject recruitment and enrollment, we will utilize recruitment flyers and approach subjects and clinicians at the Program for Traumatic Stress, in other mental health clinics, at Vet Centers and CBOC's to introduce the project and ask clinicians to refer any patients that may be interested in the study. We have developed this system of recruitment in the context of a current clinical trial.

REFERENCES AND BIBLIOGRAPHY CITED

- Aikins, D. E., Jackson, E. D., Christensen, A., et al. (2011). Differential conditioned fear response predicts duloxetine treatment outcome in male veterans with PTSD: A pilot study. *Psychiatry Res, 188*, 453-5.
- APA. (2013). *Diagnostic and Statistical Manual of Mental Disorder (5th ed.)*. Washington, DC: American Psychiatric Association.

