Data collection. The program manager (PM) will track recruitment and retention. A clinical assessor will conduct diagnostic interviews and questionnaire evaluations pre-, mid-, and post-intervention blind to group allocation. All pre-, mid-, and post-treatment biological measures will be conducted and analyzed by the psychophysiological and consultants, blind to group allocation.

Assessment, Data Collection, and Schedule. Instruments and other data collection tools and their description are in the [Assessment Detail](#). This strategy includes repeat measures yet minimizes response burden. Our goal is to test for effect signal. It is premature to evaluate durability and not ethical to keep subjects in a protocol where they may not be receiving effective treatment (particularly true of MIN), so we will not include a six-month follow-up period. Instead, a one-month follow-up will test symptoms and functioning and be utilized to re-connect participants to clinical services. Data collection at mid-point of treatment is warranted to replicate mid-treatment findings from our first trial. Such a finding may help determine dose effects and plan a dose-finding trial.

Outcome measures. The primary outcome is change in PTSD symptom severity from pre- to post-treatment. We hypothesize a large pre- to post-treatment effect for ACU ($d \geq 0.8$) and at least a mild treatment effect ($d \geq 0.30$) of the difference between groups (ACU vs MIN) pre- to post-treatment, with 80% probability of detecting a true group difference at $p < 0.05$ (2-sided). Main biological outcome (secondary outcome) is change from pre- to post-treatment in PPR (decreased startle by EMG eyeblink).

IV. Statistical Plan and Data Analyses

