General Approach. General linear mixed models (GLMM) are capable of handling multiple underlying distribution and model structures through link functions, such as repeated measures random effects models of continuous outcomes (identity link), repeated measures logistic models (logit link), and Poisson and negative binomial models (log link). In addition to modeling global fixed effects across subjects, GLMM can also model individual subject random effects. Survival analysis allows for the assessment of time to event modeling using probability estimates on survivor functions and estimates of hazard ratios. Time to event modeling using Cox proportional hazard modeling allows for all subjects to contribute information to the model up until occurrence of event, drop out, or end of study. Cox Proportional Hazards modeling will be used to investigate for effect-size of the treatment by allowing subjects to contribute their information to the model while they are being observed and censored once they are no longer being observed (loss to follow-up or end of study period). Further, using the Cox modeling we will investigate for time dependencies and informative loss to follow-up. In the case where dropouts may be associated with the treatment assignments, we will leverage intention to treat methodology and construct a piecewise random effects model with both "on-" and "off-treatment" slopes. GLMM will be used to evaluate the primary clinical hypothesized effects of treatment (ACU) on the clinical outcome of PTSD symptom severity (CAPS) over time (mid- and end-treatment, and 1-month follow-up), controlling for baseline severity of symptoms and demographic characteristics (e.g., age, gender) in comparison with placebo control group (MIN) with assumption of intent to treat. Cohen's *d* within and between subjects will be calculated. Interaction terms will be included in the models to evaluate treatment fidelity and treatment expectancy as potential moderators.

GLMM will also be used to evaluate the secondary biological hypothesized effects of treatment on pre- to post-treatment in PPR (decreased EMG eyeblink). These same statistical procedures (GLMM, survival analysis, and Cohen's *d* with intent to treat) will be applied to evaluate exploratory outcomes: clinical symptoms comorbid with PTSD, PPR (HR, HRV, SCR), and PTSD diagnosis.

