Assumptions for Power Calculations. Assumptions are based on interpolated data since primary outcomes in our first ACU study were assessed with the PSS-SR scale and there are no PTSD studies using MIN as the sham. Furthermore, to be consistent with major PTSD research, we will use the CAPS-5 (DSM-5 version) as the primary outcome, and there are as of yet no completed clinical trials using CAPS-5. In our first study, mean pre-treatment PTSD severity score was about 62% of maximum (31.55 of 51). ACU mean decreased 50% - 31.33 (10.1) to 15.65 (13.95) and wait-list mean decreased 9.3% - 30.79 (9.54) to 27.92 (12.33) at post-treatment. We thus assume that subjects will have a baseline mean CAPS-5 score of 50 (10) and a 50% reduction of symptoms and a 38% increased variance (CAPS-5 = 25; SD = 13.8) with ACU. There are sparse data about effects of MIN, noting a 33% improvement compared to pharmacological treatment only, and a 33% less effect than ACU in the Shen study. A 2010 Cochrane systematic review of over 200 trials investigating 60 clinical conditions about general placebo effect found placebos to not have important clinical effects but may influence patient-reported outcomes in some situations (e.g., pain and nausea). The pooled relative risk calculated for placebo was 0.93 (effect of only 7%) but significant. Confidence intervals are generally wide in the placebo arm. Several clinical and methodological factors were associated with higher effects of placebo. Since our study

includes some of these factors, and since we expect MIN to have some physical effect, MIN could provide an effect as much as 33% with a wider variance. This would predict mean CAPS-5 scores (MIN) at end-treatment of 33.5 (SD 15). The conservative prediction is mean CAPS-5 reductions of 25 points with ACU and 16.5 points with MIN, an 8.5-point difference with a pooled SD of 14.4. Given our experience and data about placebo effect, we can modestly expect a 12 point between group CAPS-5 difference and a pooled SD of 15.

Treatment Effects, Power and Sample Size, Primary Hypothesis. “The efficacy of verum acupuncture (ACU) for PTSD symptom severity will be large (pre- to post-treatment Cohen’s $d \geq 0.8$), and significantly better than sham acupuncture (MIN) (between group Cohen’s $d \geq 0.30$, with 80% probability of detecting a true group difference at $p < 0.05$ (2-sided).”

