Controlling for non-specific treatment-related effects. In this study, it is critical for those in the control group (MIN) to receive an equivalent amount and kind of time, empathy, setting, and assessment as those in the verum acupuncture group (ACU). Both verum and control protocols will include language currently in our acupuncture clinical trials manual for greeting, interacting with, and closing a session. Prior to the first session, each subject will meet with the acupuncturist who will conduct a Traditional Chinese Medicine (TCM) diagnostic session. A protocol example from our first acupuncture for PTSD study is Appendix A to this Attachment and included pragmatics and acupuncturist behavior. Note that this example differs in content from the proposed study. On funding, a protocol manual will be developed.

Outline of Steps of Procedures and Interventions

Step one: Conduct informed consent and conduct pre-treatment evaluation

Protocol Rev 3. 4.10.2018 MH

Step two: Randomization to group

Subjects will be allocated to group by adaptive randomization.

Step three: Begin and continue ACU or MIN interventions

Step four: After 12-week intervention, stop ACU and MIN and conduct End-Treatment Assessments

Step six: At the end of follow-up period (planned one month), determine how and where to transition subject to clinical care

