Note: One task of Data Safety and Monitoring on funding will be to review the protocol and advise the investigators about rules for continuation or discontinuation of each subject in the study and in the follow-up period. It may be unethical to continue Veterans in the follow-up period if there is no pre- to post-treatment reduction in CAPS. Furthermore, we are most interested in whether there is effect maintenance in those who have responded to treatment, so it may be scientifically meaningless in addition to the ethical dilemma to continue non-responders into the follow-up period. In this A1 revision, our primary goal is to determine if ACU provided effect (signal) compared to a placebo, and the follow-up period is not to primarily determine durability of treatment but to ensure safety and clinical follow-up planning. Our statistical methods will be able to manage data in an intent-to-treat model if subjects are withdrawn. Our current plan is to define a response as a CAPS-IV equivalent drop of 10 points (the value for CAPS-5 still needs to be determined). Those who have not had a response would have the option to withdraw and re-initiate clinical treatment immediately. Of course, any subject may withdraw at any time.

Description of Intervention Protocols

Recruitment of participants currently on medications for PTSD. It may be ideal to recruit subjects who are medication naïve, but this is not feasible in this single site study. Approximately 55% of Veterans with PTSD who are entering three of our current studies (a DoD funded multi-site trial of prolonged exposure with vs without virtual reality, [name] PI, [name], Long Beach site PI; a VA national cooperative studies program comparing prolonged exposure to cognitive processing therapy – CSP #591, [name] et al PI's, [name] Long Beach site PI and executive committee member; an industry sponsored two-site RCT of Vilazodone vs. placebo for PTSD, [name] and [name] Co-PI's) are on a medication when entering the trial, most often an SSRI. In the first two mentioned studies, the subjects can stay on the medication (with rules), and for the third study we offer a wash-out if the current medication has not been established for a long period or if effects are neutral or negative. We will thus offer a similar procedure in the proposed study to the first two mentioned studies, and the subject must be on a stable dose for 8 weeks or longer.

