Anger and Aggression. The Aggression Questionnaire (AQ) (Buss et al, 1992) has 29 items and 4 scales measuring physical aggression, verbal aggression, anger, and hostility. A total score and an inconsistent responding index (lie scale) are also derived. Cronbach's alpha for the total scale was found to be 0.85 and alphas for the scales ranged from 0.72 to 0.85. Test-retest correlations ranged from 0.72 to 0.80. The AQ will be fully administered at the primary data collection time points. To evaluate safety, ten items (1, 2, 5, 8, 11, 13, 18, 23, 25, 28) will be administered weekly as described above.

Suicidality. The Beck Depression Inventory–II (BDI-II) (Beck et al, 1996) items 9 (suicidality), 11 (agitation), and 17 (irritability), will be administered once per week as described. A score of 2 or 3 on any item will prompt further evaluation. Item 9 has been shown to be moderately correlated to the full scale Beck Scale for Suicide Ideation (Beck et al, 1988).

Satisfaction with Care. The Opinions about Care and Provider Scale is adapted from a scale developed by our research team for an NIH-sponsored study. Ten items assess opinions about care and represent satisfaction with care. Five items are designed to assess if the participant was taught specific skills.

Intercurrent Health Resource Use Inventory. This will be administered at baseline, end-of-treatment, and 6-month post treatment to help account for other non-study treatment effects.

6. Treatment Fidelity and Expectancy as Potential Moderators to Outcome

Treatment Fidelity. A Therapist Adherence Scale will be developed in the first 3 study months. It will be like one in the Appendix which was developed for computer assisted CBT

Treatment Expectancy will be assessed with The Credibility Rating Scale (Borkovec, 1972), which has been utilized in many clinical trials including other studies comparing interventions to placebo's in general.

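### Subjects without a CAPS response may withdraw before the one-month follow-up, no section keeps a one-month assessment for those who do, and one-month CAPS-5 data may therefore be lost unevenly by arm

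*Protocol*

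**What the plan says.** The rule stands in the protocol, Clinical Protocol Detail, in the note after the outline of procedure steps. The plan there is to "define a response as a CAPS-IV equivalent drop of 10 points (the value for CAPS-5 still needs to be determined"; then: "Those who have not had a response would have the option to withdraw and re-initiate clinical treatment immediately". The note calls this the current plan and gives the monitoring body the task of advising on continuation rules. It also states what the month is for: "the follow-up period is not to primarily determine durability of treatment but to ensure safety and clinical follow-up planning".

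Other sections bear on it:

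- Assessment, Data Collection, and Schedule: "a one-month follow-up will test symptoms and functioning and be utilized to re-connect participants to clinical services". The same paragraph says that there will be no six-month follow-up period.
- Outline of Steps, last step: "At the end of follow-up period (planned one month), determine how and where to transition subject to clinical care".
- General Approach, in both protocol and SAP: the mixed model evaluates CAPS "over time (mid- and end-treatment, and 1-month follow-up".
- Assumptions for Power Calculations: "we will use the CAPS-5 (DSM-5 version) as the primary outcome".
- Recruitment: data of subjects who withdraw after randomization are retained for intent-to-treat analysis. Nothing is said about collecting more.
- Assessment Detail: CAPS-5, BDI-II and the Aggression Questionnaire are scheduled at end of treatment and at one month. The Intercurrent Health Resource Use Inventory is not scheduled at one month: "This will be administered at baseline, end-of-treatment, and 6-month post treatment to help account for other non-study treatment effects".

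**The concern.** The note treats returning to clinical care and leaving study assessment as a single act, although neither requires the other. A subject who takes the option has no further scheduled study assessment. The weekly aggression and suicidality checks are tied to acupuncture sessions, which stop at week 12, so the one-month visit is the only planned study observation in a month justified by safety.

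For inference, the option is open according to the outcome, and the plan expects the outcome to differ by arm. One-month CAPS-5 could therefore be missing more often in MIN. A subject who starts other treatment in that month, whether still in the study or not, cannot be recognised from the one-month data, because the form that records non-study treatment is not given then. Its next scheduled use is a six-month visit that another section says is not included.

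The response definition also refers to a CAPS-IV equivalent while the trial administers CAPS-5. The protocol openly lists the conversion as outstanding, and neither document supplies it.

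**Working it through.** **Inputs from the plan** (Assumptions for Power Calculations; Sample size needed and power): baseline CAPS-5 mean 50, SD 10; end of treatment ACU 25 (SD 13.8) and MIN 33.5 (SD 15); so mean drops of 25 and 16.5 points; pooled SD 14.4; 45 per arm; two-sided alpha 0.05; power 0.80.

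**Assumptions not in the plan:** normally distributed change; pre-post correlation r of 0.3, 0.5 or 0.7; a CAPS-5 cut-off c of 5 or 10 points, used only as sensitivity values.

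**Reproducing the plan's figure.** Total N = 4 × [14.4 × (1.960 + 0.842) / 8.5]² = 90.1, against the stated 90 (92 if each arm is rounded up). The inputs are therefore read as the plan uses them.

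**Share eligible to leave.** SD of change = √(10² + s² − 2·r·10·s), with s = 13.8 for ACU and 15 for MIN. Share = Φ((c − mean drop) / SD of change).

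Example at r = 0.5, c = 10:

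- ACU: SD = √(100 + 190.44 − 138) = 12.35; Φ((10 − 25)/12.35) = Φ(−1.215) = 11.2%.
- MIN: SD = √(100 + 225 − 150) = 13.23; Φ((10 − 16.5)/13.23) = Φ(−0.491) = 31.2%.

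| r | c | ACU | MIN | MIN/ACU | of 45: ACU, MIN |
|---|---|---|---|---|---|
| 0.3 | 5 | 8.3% | 22.7% | 2.7 | 3.7, 10.2 |
| 0.3 | 10 | 14.9% | 33.6% | 2.3 | 6.7, 15.1 |
| 0.5 | 5 | 5.3% | 19.2% | 3.6 | 2.4, 8.7 |
| 0.5 | 10 | 11.2% | 31.2% | 2.8 | 5.0, 14.0 |
| 0.7 | 5 | 2.1% | 14.2% | 6.7 | 1.0, 6.4 |
| 0.7 | 10 | 6.4% | 27.2% | 4.2 | 2.9, 12.2 |

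The 6.7 uses unrounded shares (0.1418/0.0213); the rounded percentages give 14.2/2.1 = 6.8. In every row MIN exceeds ACU, by 12 to 21 percentage points.

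**Extreme case for a completer summary.** Suppose every eligible subject leaves, the one-month score equals the end-treatment score, and only those who remain are compared. At r = 0.5 and c = 10 the retained means are 22.9 (ACU) and 27.7 (MIN). The difference is then 4.8 points instead of 8.5. Over the six rows it runs from about 4.7 to 6.1. This does not describe a mixed model that also uses the end-treatment scores.

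**Is non-response the same as remaining severe?** The entry threshold is a CAPS-5 total of at least 26. On the plan's end-treatment figures, the share at or above 26 is Φ((33.5 − 26)/15) = Φ(0.50) = 69% in MIN and Φ((25 − 26)/13.8) = Φ(−0.07) = 47% in ACU. Both far exceed the non-responder shares above, so most subjects still above the threshold would count as responders and have no such option.

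**The case against.** A reader might infer that the patients most at risk go unassessed, or that those who still have full PTSD are the ones who skip the visit. The documents do not support either. Withdrawal is an option, and it follows an end-treatment visit with CAPS-5, BDI-II and the Aggression Questionnaire. Those who leave do so to resume treatment. No section ranks non-responders as the highest safety risk: Human Subjects Detail says only that non-effectiveness is more likely in MIN. The calculation above also shows that a small drop is different from a high remaining score.

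A reader might also infer that the primary result is biased. The primary outcome is pre- to post-treatment change, which is observed before the option applies. If leaving depends only on recorded CAPS-5 scores, the data are missing at random, and a likelihood-based mixed model that includes those scores can remain valid. The plan also names on- and off-treatment slopes and a check for informative loss to follow-up.

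The rule is provisional, with monitoring advice still to come, and the missing CAPS-5 value is declared. The sections on transition to care can be read as a default with an exception.

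Most of this stands, and it narrows the point. It does not supply a one-month assessment for those who leave. The on/off-treatment model is named without detail, and a subject who leaves after the end-treatment visit contributes no later observation to it. The missing-at-random argument does not cover leaving for unrecorded reasons or treatment that nobody records.

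**Conclusion.** The point holds as a gap in one-month data collection. Under the plan's own means and SDs, and the assumed correlations and cut-offs, 2% to 15% of ACU and 14% to 34% of MIN would be eligible to leave. Because uptake is not stated, these shares are the most that the option itself could remove; the actual loss may be much smaller. The direction, more in MIN, held in every case tried and agrees with the plan's own expectation.

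What is exposed is the one-month estimate, any summary of completers at that visit, and the interpretation of one-month scores where new treatment is unrecorded. The planned 10% attrition is applied to the end-treatment comparison, so it is not a direct benchmark for this loss. This is a low-cost improvement to the design. The unset CAPS-5 value is an acknowledged open item.

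**What to change.** In the note in Clinical Protocol Detail, separate the two acts. State that stopping study participation to resume clinical care does not by itself end data collection. Ask such subjects to complete the one-month CAPS-5, BDI-II and Aggression Questionnaire already scheduled, unless they withdraw consent for data collection.

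Add the existing Intercurrent Health Resource Use Inventory to the one-month column of the assessment schedule, so that treatment started in that month is recorded.

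The sponsor should also reconcile the schedule section, the outline of steps and the note on when transition to care occurs, and reconcile the CAPS-IV response definition with the CAPS-5 used in the trial. No cut-off or clinical rule is proposed here.

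The cost is protocol wording, one existing form at an existing visit, and a few minutes of extra burden for subjects. Some one-month values will be recorded on non-study treatment, which the added form makes visible.
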